## 3) Background

Children with ASD can be accurately identified as early as two years old. Children identified early and placed promptly into comprehensive treatment models [CTMs] such as applied behavioral analysis programs, show improvements in language, IQ and adaptive functioning. Still, average age of ASD diagnosis in the US is around 4 years old, and is older for low-income and racial/ethnic minority children. Low-income and minority children are also less likely to be diagnosed with ASD, and are more likely to have severe features (e.g. comorbid intellectual disability). Although access to evidence-based ASD therapy is rapidly expanding, most children with ASD are not treated with evidence-based interventions, and minority children use Early Intervention and CTM therapies at the lowest rates. Thus, there is a strong need for interventions that connect low-income and minority children with existing services that they are eligible for and could access. Primary-care based screening for ASD and other developmental delays is increasing. As a result, more children with suspected ASD are identified and referred from primary care. However, unlike other conditions for which early identification and treatment are critical (e.g., hearing impairment, congenital metabolic disorders), there exist no statewide or national systems to ensure that children identified with ASD risk are promptly evaluated and treated. While ASD services are theoretically available for most children in the US, they are often not accessed, leaving a critical gap between identification of suspected ASD in primary care and access to ASD diagnostic and treatment services, particularly for low-income and minority children. Research by our team suggests that this gap exceeds 2 ½ years on average. However, our prior research has also shown that when PCPs help families connect with ASD services, ASD diagnosis and treatment is timelier, and timely diagnosis is associated with increased use of evidence-based services. As a result, we propose a model statewide intervention to close the gap between identification of suspected ASD in safety-net (i.e., underserved setting) primary care clinics and use of diagnostic and treatment resources, for low-income and minority children.

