## 5) Study Population

### a) Number of Subjects

The three subject groups include clinics, child/parent dyads, and providers. We seek to enroll 7 safety net primary care practices. 70 child/parent dyads will participate in this study (20–baseline condition, 25–intervention, 25–control). We estimate that 30 providers will participate in this study (15–intervention; 15–control). The number of participants per site will depend on the size of the participating clinics.

Per the expansion to all of Portland-metro area, we estimate that there will be around 300 children enrolled in the next 3 years.

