### b) Inclusion and Exclusion Criteria

There are different eligibility requirements for clinics, children/parents, and providers.

To meet eligibility criteria, participating clinics must have >30% Medicaid enrollees or uninsured patients. Family medicine clinics must have >30% children. The study will be initially offered to safety-net primary care practices in 3 Oregon counties. We seek to enroll 6 clinics; if more than 6 clinics initially express interest, we will randomly choose 6 interested clinics, reserving at least two spots for non-metropolitan clinics. If fewer than 6 express interest, we will open recruitment to an additional two counties. Additional counties will be considered if recruitment is inadequate.

Child/parent dyads are eligible for inclusion when the child's PCP suspects the child has ASD. This can be for any reason, including the child having a high-risk ASD screen, or clinical concern. Children with prior ASD diagnoses or prior history of diagnostic evaluation for ASD are excluded. Enrolled children must be between age 12 and 54 months at enrollment to ensure EI/ECSE eligibility.

Provider subjects must be pediatric primary care providers (e.g., physician, nurse practitioner, physician assistant) licensed in Oregon, and must see children age 1-5 for well-child care. Subspecialists are excluded.

For the expansion, any child aged 1-5 years old on an Autism clinic waiting list at OHSU, Randall Children's Hospital, Providence Child Development Institute, Mindsights, or The Children's Program, or a referral from an Autism ALERT trained provider is eligible to join the study, if they have not previously been medically diagnosed with Autism.

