informing them of the upcoming survey and the \$10 incentive for completion. A \$10 cash or gift card incentive will be provided for survey completion. The survey will initially be sent 3 times via a secure RedCap link. Then non-responders will be contacted via telephone. Subjects who do not respond to either email or telephone will be sent a survey mailing with a \$5 Dutch Bros coffee card. The survey will be marked with a study number only and will contain no personal identifiers. The study team will have a separate locked document that has the key linking study ID to personal information (see below). Completed surveys will be mailed back to the study team in an envelope and entered into a secure database behind the OHSU firewall. Original copies will be stored in a locked file cabinet in the study team area.

Study team members will also be reaching out to families via email and/or phone, about participating in a semi-structured phone interview regarding their experiences with navigators, and the overall Autism diagnosis process. Families will be contacted via email and telephone to schedule these interviews. Participating families will receive \$50 for completing the interview. Interviews will be recorded using WebEx or a digital audio recorder. These recordings will then be sent to GMR Transcription (HIPAA-compliant) to provide transcripts. Finally, the study team will code the interviews using Dedoose software to get a better understanding of parents' experiences in the Autism evaluation process.

Administrative data about children from the ecWeb (EI/ECSE) database will be governed by a Data Use Agreement (DUA) between [name] (PI) and the Oregon Department of Education (ODE). Consistent with our prior DUA's, we will request ecWeb access for only families with signed consent and a FERPA release for each child's educational data. The study team will submit names and dates of birth of people who signed consent and authorization to ODE staff, and ODE staff will allow the study team direct access to these individuals' data within ecWeb, ODE's database for Early Intervention. ODE staff are only releasing data and will not be considered engaged in research. These data include details on the dates and times of each child's referral, evaluation, and service plan. ODE staff will provide access to these data, which study team members will analyze, and are not considered part of the study team.

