We will compare efficacy outcomes in the Autism ALERT group to the baseline and control groups, using bivariate analyses and Kaplan-Meier curves for time to treatment variables. Estimated effect sizes for the subsequent R01 will be measured using Cohen's d. To test engagement of target mechanisms, we will assess whether efficacy outcomes differed by mechanistic outcome (e.g., whether parental stress was associated with time to treatment), using bivariate or limited multivariable models. We will also assess whether outcomes differ according to family demographic characteristics, both overall and by study arm, to test variability in intervention effects. Secondary and exploratory efficacy outcomes from ecWeb and Medicaid claims will be analyzed in the same framework.

Fidelity outcomes include both structural measures (e.g., receipt of program components) and procedural measures (e.g., quality of delivery of these components). We will use descriptive

statistics to assess delivery of the START Autism ± Autism ALERT training curriculum components. We will also use descriptive statistics to calculate navigator fidelity to the protocol, using the Navigator Fidelity Checklists. Checklists will also be cross-checked with recorded calls to assure accurate documentation. We will use descriptive statistics to characterize PCP use of the Autism ALERT website. To understand how Autism ALERT and START Autism altered PCP screening and referral behaviors, we will assess rate of ASD screening and EI/ECSE referral in both study arms in the baseline condition, and 3-and 6-months after initiation of START Autism ±Autism ALERT. As an exploratory analysis, we will assess whether racial/ethnic or language differences in PCP screening are present, and whether they vary by study arm or by PCP/clinic characteristics.

Our goals in this pilot study are to assess the feasibility and acceptability of the intervention and analysis, develop hypotheses regarding mechanism of action, and to provide context for defining meaningful differences and otherwise inform R01 power calculations. We intentionally have not powered to detect statistically significant differences. However, estimates will provide preliminary evidence of intervention effects, generate effect size estimates, and will help refine analytic strategy, efficacy hypotheses, and sample size estimates for a larger study.

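### The pilot's efficacy contrasts and the Cohen's d passed to the R01 are unadjusted; child age, already recorded over a 12-54 month range, should be added as one prespecified covariate beside them

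*Protocol*

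**What the plan says.** Protocol section 8 (Data Analysis) fixes the method for the efficacy contrasts: "We will compare efficacy outcomes in the Autism ALERT group to the baseline and control groups, using bivariate analyses and Kaplan-Meier curves". It continues: "Estimated effect sizes for the subsequent R01 will be measured using Cohen's d".

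Models with more than one variable appear for other purposes. For mechanism, the question is "whether parental stress was associated with time to treatment), using bivariate or limited multivariable models". For demographics, the plan is: "We will also assess whether outcomes differ according to family demographic characteristics, both overall and by study arm, to test variability in intervention effects". That second analysis looks for variation in effect and does not adjust the arm contrast.

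On age, section 5b says: "Enrolled children must be between age 12 and 54 months at enrollment to ensure EI/ECSE eligibility". Section 6 shows that birth dates are held: "The study team will submit names and dates of birth of people who signed consent and authorization to ODE staff". Section 4 randomizes clinics by coin flip, stratified by size and urbanicity only. Section 5a gives the group sizes: "70 child/parent dyads will participate in this study (20–baseline condition, 25–intervention, 25–control". Section 2 names the efficacy outcomes as educational evaluation within six months and time from referral to treatment. Sections 4 and 8 make efficacy preliminary and deliberately unpowered.

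**The concern.** The age window covers 42 months of early childhood. Section 3 says that ASD can be identified from about age two and that "average age of ASD diagnosis in the US is around 4 years old". It is therefore plausible that a child referred near the lower limit and one referred near the upper limit differ in how soon they are evaluated or treated. With 25 dyads per arm in three clinics per arm, mean age may differ between arms, and a bivariate contrast carries that difference into the estimate.

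Two features add to the case. First, clinics are assigned before children are referred. Families enter when their primary care provider suspects ASD, no masking of providers is described, and section 5e reports that enrollment lagged in the control arm. Age mix could therefore differ through recruitment as well as by chance. Second, the 20-dyad baseline group is not one of the two randomized arms, so randomization does not protect its comparison with ALERT at all.

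What is at stake is the effect size that section 8 intends for planning the next trial.

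**Working it through.** The protocol states no power, SD, ICC or effect size, so there is no figure of its own to reproduce. The group sizes add up (20 + 25 + 25 = 70).

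**Inputs from the protocol:** 25 dyads per arm; 3 clinics per arm (section 4; section 5a also mentions 7 practices, and I use the 6 of the design section), so 25/3 = 8.33 dyads per clinic; ages 12-54 months.

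**Assumed inputs:** the age SD, the clinic ICC for age, the strength of the age effect, and the evaluation rate.

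**1. Chance difference in mean age.**
- Evenly spread ages: SD = 42/√12 = 12.1 months.
- SE = 12.1 × √(2/25) = 3.43 months; 95% range ±1.96 × 3.43 = ±6.7.
- With clustering, the variance is multiplied by 1 + 7.33 × ICC. At ICC 0.05 this is 1.367, so SE = 3.43 × √1.367 = 4.01 and the range is ±7.9.

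| Age SD (assumed) | ICC (assumed) | 95% range, months | P(gap > 6 months) |
|---|---|---|---|
| 12.1 | 0 | ±6.7 | 8.0% |
| 12.1 | 0.05 | ±7.9 | 13.4% |
| 12.1 | 0.10 | ±8.9 | 18.4% |
| 10 | 0 | ±5.5 | 3.4% |
| 10 | 0.10 | ±7.3 | 10.7% |
| 8 | 0 | ±4.4 | 0.8% |
| 8 | 0.10 | ±5.8 | 4.4% |

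A simulation with evenly spread ages and no clustering gave 8.0% and a 95th percentile of 6.7 months, in agreement with the first row.

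**2. Effect on Cohen's d of a 6-month gap.** Shift = r × 6/12.1, where r is the assumed age-outcome correlation. This gives 0.05 (r = 0.1), 0.15 (r = 0.3) and 0.25 (r = 0.5). The SE of d is about √(2/25) = 0.28.

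**3. Effect on the six-month evaluation difference of a 6.7-month gap.** Assume the log-odds change by 0.5 or 0.8 per year of age. The shift in log-odds is 0.5 × 6.7/12 = 0.28 or 0.8 × 6.7/12 = 0.45. Centred on an evaluation rate of 50%, this is 7.0 or 11.1 percentage points. Centred on 20% or 80%, it is about 4.5 or 7.2 points. At a 50% rate the SE of the difference is √(2 × 0.25/25) = 14 points before clustering.

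**4. What adjustment gains, ignoring clustering.** For a continuous outcome the SE is multiplied by √(1 − r²), which is equivalent to 25/(1 − r²) dyads per arm.
- r = 0.1: SE falls 0.5%; 25.3 per arm.
- r = 0.3: SE falls 4.6%; 27.5 per arm.
- r = 0.5: SE falls 13.4%; 33.3 per arm.

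For the six-month evaluation I simulated the unadjusted risk difference against one standardised from a logistic model (evenly spread ages, 50% rate, no arm effect, no clustering). The variance gain was about 0% at 0.3 per year, 4-5% at 0.5 and 13-15% at 0.8.

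**The case against.** The strongest reply is that nothing in the plan is wrong. The primary outcomes are feasibility and acceptability, section 8 declines to power for efficacy, and one stated purpose is to refine the analytic strategy for a later trial. A bivariate summary is defensible for a six-clinic pilot. Covariate lists are often left to a statistical analysis plan, which is not at hand. The expansion has no control arm, so the point concerns the pilot comparisons only. All of this stands and limits the weight of the point. Even so, section 8 positively specifies bivariate methods for these contrasts, so this is a stated choice and not a silence.

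A reader might also infer three stronger claims. The protocol supports none of them.
- *Age strongly affects these outcomes.* Section 3 gives a national average age at diagnosis and an earliest age of identification. Neither says how age changes the chance of evaluation within six months among children who are already suspected, not previously evaluated, and inside a window chosen for service eligibility. Neither strength nor direction is documented.
- *An age gap of more than half a year is likely.* It is possible, but even with evenly spread ages its probability is 8-13% at an ICC of 0 to 0.05. At SD 10 without clustering it falls outside the 95% range.
- *The randomised contrast is biased.* Chance imbalance is already part of its sampling error. The shifts in steps 2 and 3 are below one SE.

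**Conclusion.** The point holds as a modest improvement. The ALERT-control and ALERT-baseline contrasts, and the d derived from them, ignore one covariate that is already collected, wide in range, unstratified and plausibly prognostic.

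The size depends on assumptions that the protocol cannot settle. A chance age gap at or near the edge of the 95% range would move the result by anything from a negligible amount to about 0.25 in d, or by roughly 4-11 points in the evaluation rate. The upper end needs a wide age spread, a strong age effect and an evaluation rate near 50%. For the randomised contrast the benefit is mainly precision, from nothing to the equivalent of about 8 more dyads per arm (33.3 − 25) at r = 0.5. Adjustment also gives some protection against age differences arising from recruitment after clinic assignment, and against non-random differences in age between ALERT and baseline. It would not remove other differences between those two groups.

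**What to change.** For the pilot comparisons, name age in months at enrollment as the single prespecified covariate, and report an age-adjusted estimate beside each bivariate one:

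- evaluation within six months: a standardised risk difference from a logistic model with arm and age;
- time to treatment: an age-adjusted hazard or rate ratio beside the Kaplan-Meier curves;
- continuous outcomes: d from the age-adjusted mean difference, divided by the unadjusted pooled SD so that both versions of d share a scale.

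Inference should allow for the six clinics. One option is to compare clinic-level averages of age-adjusted residuals between arms, with 6 − 2 = 4 degrees of freedom; uncorrected robust standard errors are unreliable with so few clusters. Tabulate age by group. Keeping both estimates matters because ALERT could itself change the age at which children are referred, and the adjusted and unadjusted contrasts would then answer different questions.

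The cost is a few lines of analysis on data already held and one covariate in a sample of 50 randomized-arm dyads. If age proves weakly prognostic, little is gained. No further covariates should be added at this sample size.

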## 2) Objectives

Autism Access Link for Early Referral and Treatment [ALERT], the intervention proposed in this application, is a novel state-wide referral and case management platform that PCPs can activate to ensure that a child with suspected Autism Spectrum Disorder (ASD) receives all necessary ASD diagnosis and treatment resources in a single referral, radically simplifying a complex diagnostic and treatment process. We hypothesize that Autism ALERT will have strong acceptability and high rates of use among primary care providers as well as among diverse low-income patients of children at risk for ASD, and that we will see higher rates of child ASD educational evaluations within six months, and shorter time between referral and ASD treatment,.

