## 4) Study Design

We propose a pilot clustered interventional trial with two arms. Clinics in the intervention arm receive Autism ALERT plus an ASD screening intervention (START Autism), and clinics in the comparison intervention (control) arm receive only START Autism (no Autism ALERT). As this is a pilot trial, primary outcomes of interest are feasibility and acceptability. We will additionally assess mechanism of outcome, preliminary efficacy, and protocol fidelity. Feasibility and acceptability will be assessed in intervention clinics. Mechanism of action and preliminary efficacy will be assessed by comparing intervention to control clinics. Fidelity is assessed in both arms. We will pilot test Autism ALERT in 6 safety-net primary care clinics in Oregon: 3 clinics will serve as intervention clinics, receiving both Autism ALERT and START Autism, and 3 clinics will serve as controls receiving START Autism only. Study arm will be assigned via coin-flip randomization of clinics, stratified for size and urbanicity, by a statistician who is not otherwise part of the study team.

In 2023 we received new funding from CareOregon to expand the project. As a result, this pilot study will be expanded to all of Portland-metro area. It will no longer include a control arm. Participants will be recruited off of Autism clinic waiting lists in the PDX metro area, and will be enrolled into the study to receive family navigation services from our partners at Help Me Grow.

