## **8) Data Analysis**

Process data from CCMT and Navigator Fidelity Checklist will be used to calculate contact attempts, time to first contact, total time spent per family, and counts of specific navigator activities. Families who complete all calls will be compared to those who broke off contact, and specific points of participant drop-off will be calculated. We will assess whether specific intervention activities varied by family demographic characteristic and clinic site, to assess variability in acceptability, using bivariate analyses. Family survey data will also be used to assess feasibility and acceptability. Initial analyses will focus on families who participated in ALERT, assessing experience of care and improvement suggestions. Next, post-intervention family experience will be compared in intervention vs. control clinics using bivariate analyses with an intention-to-treat approach. We will also examine variation in experience outcomes overall, and by study arm, by demographic characteristics, in order to assess whether the intervention was appropriate for diverse families, and to target improvements. Parent responses to open-ended items will be assessed via conventional content analysis. Using the parent interviews, we will also qualitatively assess families' feelings towards the evaluation process, and for the intervention arm we will also be looking at experiences with family navigators.

PCP process data will be used in a similar fashion. PCP/Navigator interactions will be descriptively characterized, using the PCP-Navigator Con-tact log and use of the PCP Website. PCP survey data will be used to characterize PCPs' post-intervention experiences. PCPs' overall experiences will be compared in both arms using bivariate testing, and open-ended questions will be coded.

We will refine our mechanism hypotheses and measurement by examining change in family-and provider-reported outcomes (e.g., stress, empowerment) pre-and post-intervention, in both study arms, primarily using descriptive and bivariate tests. Exploratory analyses will assess whether mechanism outcomes differ by family race/ethnicity, English proficiency, or insurance type, both overall and by study arm, using bivariate or limited multivariable regression analyses. This will allow us to gather valuable descriptive data on variation in engagement of target mechanisms, which might allow for individualized messaging in future research.

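### Cohen's d is named as the R01 effect size with no outcome excepted, but it suits neither efficacy hypothesis: a censored time to treatment and a six-month evaluation rate

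*Protocol*

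**What the plan says.** Section 2 of the Protocol (Objectives) puts forward two efficacy hypotheses: "higher rates of child ASD educational evaluations within six months" and "shorter time between referral and ASD treatment". The first is a yes/no outcome per child and the second is a time to an event.

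Section 8 (Data Analysis) compares efficacy outcomes in the ALERT group with the baseline and control groups "using bivariate analyses and Kaplan-Meier curves for time to treatment variables". The next sentence reads "Estimated effect sizes for the subsequent R01 will be measured using Cohen's d". It names no outcome to which it is limited. Later in the paragraph, the secondary and exploratory outcomes from ecWeb and Medicaid claims are placed under the same framework. The Protocol names no hazard ratio, restricted mean, risk difference or odds ratio.

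Continuous scores come earlier in section 8, in the mechanism analysis: "examining change in family-and provider-reported outcomes (e.g., stress, empowerment) pre-and post-intervention".

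The pilot is also meant "to provide context for defining meaningful differences and otherwise inform R01 power calculations". It is deliberately not powered, and section 4 states "As this is a pilot trial, primary outcomes of interest are feasibility and acceptability".

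**The concern.** Using Kaplan-Meier implies that some children will still be untreated when observation ends. Cohen's d needs a mean and a standard deviation that include every child, so somebody must decide what value an untreated child receives and where follow-up is cut. The Protocol fixes neither for this outcome. Two analysts with the same data could therefore report different values of d, and neither value would carry over to a trial with a different follow-up. A hazard ratio does carry over, provided hazards are roughly proportional.

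For the six-month rate, a d computed on a 0/1 variable is the risk difference divided by a standard deviation that is itself fixed by the two rates. Different pairs of rates can give the same d, so d alone does not return the control rate and the difference that a two-proportion sample size needs.

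At stake is the usefulness of the pilot's effect sizes for the R01, which is one of its stated purposes.

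**Working it through.** The Protocol states no effect size, median, hazard ratio or cut-off for time to treatment, so there is no figure to reproduce. What follows shows the mechanism under assumed inputs.

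**From the Protocol.** About 25 dyads per arm in the controlled comparison (section 5a). The family survey is at 6 months (section 6). The gap from suspicion to services averages more than 2½ years (section 3).

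**Assumed.** Exponential times, proportional hazards, no clustering; hazard ratio (HR) 1.5 or 2; control median m of 6, 9, 12 or 30 months; cut-off T of 6 or 12 months; two-sided 5% level and 80% power. The 30-month median is suggested by section 3, which gives an average rather than a median. An exponential time with mean 30 months has median 30 × ln 2 = 20.8 months, inside the range used.

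**Formulas.** λ0 = ln 2/m and λ1 = HR × λ0. Untreated children are set to T:
- mean = (1 − e^(−λT))/λ
- mean square = 2[1 − e^(−λT)(1 + λT)]/λ²
- d = difference in means / √(average of the two variances)
- n per arm from d = 2(1.960 + 0.842)²/d²
- log-rank n per arm = [4(1.960 + 0.842)²/(ln HR)²]/(p0 + p1), where p = 1 − e^(−λT). For HR 2 the numerator is 65.35 events.

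Sample sizes are rounded to the nearest whole number.

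**Median 9 months, HR 2.**
- T = 6: means 4.805 and 3.916, SDs 1.879 and 2.143, so d = 0.889/2.015 = 0.441 and n = 81. With p0 = 0.370 and p1 = 0.603, log-rank n = 65.35/0.973 = 67.
- T = 12: means 7.831 and 5.470, SDs 4.286 and 4.070, so d = 2.36/4.179 = 0.565 and n = 49. With p0 = 0.603 and p1 = 0.843, log-rank n = 65.35/1.446 = 45.

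The true HR is 2 in both rows. If untreated children were dropped instead, d would be about 0.13 and 0.26.

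**Other scenarios.**

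| Median / HR | d at 6 | d at 12 | n from 6-month d | 12-month log-rank n | Ratio |
|---|---|---|---|---|---|
| 6 / 1.5 | 0.283 | 0.351 | 196 | 118 | 1.7 |
| 6 / 2 | 0.515 | 0.624 | 59 | 39 | 1.5 |
| 9 / 1.5 | 0.241 | 0.313 | 269 | 141 | 1.9 |
| 9 / 2 | 0.441 | 0.565 | 81 | 45 | 1.8 |
| 12 / 1.5 | 0.214 | 0.283 | 344 | 167 | 2.1 |
| 12 / 2 | 0.391 | 0.515 | 103 | 52 | 2.0 |
| 30 / 1.5 | 0.141 | 0.194 | 795 | 328 | 2.4 |
| 30 / 2 | 0.257 | 0.354 | 238 | 98 | 2.4 |

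The rise in d runs from 0.624/0.515 = 1.21 to 0.354/0.257 = 1.38, that is 21% to 38%.

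**Mismatched horizons (median 9, HR 2).** Taking the 6-month d into a 12-month R01 gives 81 per arm where 45 would do. Taking the 12-month d into a 6-month R01 gives 49 where 67 are needed: events = 49.2 × 0.973 = 47.9, and power = Φ(√(47.9/4) × 0.693 − 1.960) = 0.67.

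**Same horizon.** At median 9 and HR 2 the comparison is 81 against 67 at 6 months (about 20% more) and 49 against 45 at 12 months (about 9% more). The gap widens with heavier censoring. At median 30 and HR 2, the 6-month log-rank n is 65.35/(0.129 + 0.242) = 176, against 238 from d (35% more). In these examples the error is towards too many children, not too few.

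**Precision with 25 per arm (T = 6, median 9, HR 2).** SE(d) = √(2/25 + 0.441²/100) = 0.286, so the 95% CI for d is −0.12 to 1.00. Expected events are 25 × 0.370 = 9.3 and 25 × 0.603 = 15.1, so SE(ln HR) = √(1/9.3 + 1/15.1) = 0.417 and the 95% CI for the HR is 0.88 to 4.5. Both ignore clustering by clinic.

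**The case against.** The strongest reply is that the fault is inferred. The sentence does not expressly apply d to time to treatment. That outcome has its own survival method, and d may be intended only where a difference in means makes sense. Matching estimators to outcomes is also commonly left to a SAP, which was not available here. Part of this stands: a reader might infer that the investigators will average truncated times or discard untreated children, and nothing in the Protocol says so. What does not stand is the plea of missing detail. The Protocol positively names one measure, in the efficacy paragraph, where neither section 2 hypothesis is an uncensored continuous score. If a narrower use is meant, one edit makes it explicit.

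A second reply is that nothing is lost. Individual times are kept, a hazard ratio can be computed later, and section 8 presents the estimates as provisional. That is fair and limits the weight of the point.

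A third is that the large sample-size contrasts need the pilot and the R01 to use different horizons, and the Protocol gives no R01 follow-up. That also stands. A reader might infer that the R01 will be badly mis-sized, but the documents do not support that. Sampling error with 25 per arm is also larger than the shift from 0.44 to 0.57. Imprecision does show in a confidence interval, whereas dependence on an unstated cut-off does not.

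A d converted from a log hazard ratio would avoid the problem under proportional hazards, but the Protocol names no such conversion.

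**Conclusion.** The point holds and is minor. As written, the effect-size sentence reaches a censored time and a binary rate, and d suits neither. For the time, d moved by about 21% to 38% between 6 and 12 months in every scenario tried, with the hazard ratio held fixed. These figures rest on exponential times, proportional hazards, no clustering and assumed medians and hazard ratios, and they are illustrations rather than bounds.

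Only R01 planning is affected. The pilot's conclusions on feasibility and acceptability are untouched. The expansion has no control arm and is to be analysed mainly descriptively, so the point concerns only the controlled pilot comparison. Nor is d itself wrong: it is reasonable for scores such as stress and empowerment. Changing the measure gives a scale that can be carried forward. It does not give more precision.

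**What to change.** Amend the effect-size sentence in section 8 so that it assigns a measure to each type of outcome:
- continuous scores (such as stress and empowerment): Cohen's d;
- time from referral to ASD treatment: a hazard ratio with 95% CI, or a restricted-mean difference with 95% CI at a horizon fixed in advance. The horizon must be fixed because this difference also moves with it (0.89 months at 6 and 2.36 months at 12 in the median-9, HR 2 example);
- educational evaluation within six months: a risk difference with 95% CI. This should be required, since otherwise limiting d would leave the second efficacy hypothesis with no effect size.

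State also which planned data define treatment. Section 6 says of ecWeb: "These data include details on the dates and times of each child's referral, evaluation, and service plan". A treatment start date is not in that list, so the endpoint should be tied to the service-plan date or to the Medicaid claims mentioned in section 8. On that condition no new data are needed.

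The cost is a few lines of text. Effects will no longer share one common scale, and the hazard ratio assumes roughly proportional hazards.
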